We are postulating that by application of CGMS for 2 weeks glycemic patterns of individual patients will be identified and the education provided in this regard will change the insight of the individual towards his disease which will culminate in better longer term blood glucose control and already previous studies have shown that glucose readings from the most recent 14 days correlate strongly with 3 months of mean blood glucose, time in ranges, and hyperglycemia metrics (33,34).

Primary objective:

To study the effects of rtCGM vs isCGM on:

- Reduction in HbA1c (at the end of 3 months).

Secondary objectives:

- Reduction in glycemic variability.
- Reduction in hypoglycemic events in adults with Type-1 Diabetes.
- Reduction in Fructosamine (at the end of 2 weeks).
- Quality of life as assessed by QOLID (Nagpal etal) Questionnaire

MATERIALS AND METHODS

1. **Study design:** Open label crossover RCT with 3 arms
2. **Sample size:** Sample size of 17 is requires for a power of 80% to detect 0.5% change in HbA1c between both groups with an alpha of 0.05, Assuming 10% attrition in each group 20 patients will be recruited in all rt-CGMS and is-CGMS and 40 in SMBG arms.
3. **Subjects:** Patients attending Endocrinology OPD at PGIMER Chandigarh
4. **Study Period:** 15th June 2023 to 15th February 2024(last enrolment on 15th August 2023) and last follow up on 15th February 2024.
5. **Study Center:** PGIMER, Chandigarh
6. **Study Population:** Patients who fulfill inclusion and exclusion criteria will be recruited from OPD.

Inclusion criteria :

- Adolescents and adults ≥ 15 years with Type-1 Diabetes mellitus defined by any of the following;
 - Diabetic Ketoacidosis or ketonemia or ketonuria at diagnosis with insulin dependence for survival since diagnosis OR
 - Insulin dependence for survival since diagnosis and any one of the following autoantibody positivity: GAD-65 or IA-2
- Patients on Basal bolus regimen (**Glargine as basal and lispro/Aspart/Glulisine as bolus**);
- Duration of Diabetes > 2 years;

- Insulin dose requirement of at least 0.5U/kg
- HbA1c 8%-12%;
- Gold score<4;
- No previous experience with rt-CGMS and/or is-CGMS;
- Euthyroid status;
- If hypothyroid, then on stable dose of Levothyroxine for last 3 months with normal T4 level;
- Urine albumin creatinine ratio<300 mg/g of Creatinine;
- Those willing to give informed consent prior to enrolment.

EXCLUSION CRITERIA:

- LADA or Secondary Diabetes
- eGFR<60ml/min/1.73 m^2
- Celiac disease;

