- Hb<12g/dl for males and <11g/dl for females;
- Hypoglycemia unawareness defined by Gold score \geq 4;
- HbA1c>12%;
- DKA in previous 3 months;
- Severe Non proliferative Diabetic retinopathy/Proliferative DR/Macular edema;
- Pregnancy;
- Lactation;
- Willing to become pregnant during study;
- Requiring MRI for any existing condition;
- Any chronic illness.

METHODOLOGY

Participants meeting inclusion criteria will be randomized to rt-CGMS, is-CGMS and SMBG arms. Randomization will be done using computer generated random number list. Blocks of patients with HbA1c 8%-10% and 10%-12% will be distributed equally in all 3 groups.

Sample Size: With a 1:1:2 randomization ratio in 3 arms with sample size of 20:20:40 participants in each groups will be required.

Initial training of 2 weeks for all enrolled patients in each of 3 groups about the disease itself, ICR, ISF, carbohydrate counting and bolus dose adjustment based on these parameters will be done, for premeal boluses. **Only those patients will be enrolled who are using Lispro/Aspart/Glulisine for their diabetes control.** All adults enrolled in the rt-CGM group will be placed on rt-CGM Medtronic CGMS for 2 weeks and finger-prick blood glucose will also be monitored by glucometer (SMBG) 3 times on day 1 and then at least 2 times per day with proper record of time. All patients will use same glucometer for SMBG. Physical exercise of at least 30 mins aerobic activity will be required in all patients.

After a week a new Medtronic CGMS will be applied as per the manufacturer recommendation. Those randomized into is-CGM will be placed on Abbott Libre Flash system for 2 weeks. A 3rd group on SMBG will also be there (doing SMBG 4 times a

day- Before breakfast, Before Lunch, and Before Dinner and post meal (after any one meal on rotational basis) and **7 point profile once a week on Sunday**).

During this 2 week intervention phase all the patients will be monitored daily telephonically along with once in a week follow-up visit.

Fructosamine assay will be repeated after 2 weeks in rt-CGMS and is-CGMS groups and glycemic control compared. Thereafter the 3 groups shall use SMBG for monitoring glycemic status as in SMBG group and HbA1c will be repeated at the end of 3 months.

CGMS metrics of the 2 weeks (TBR, TIR ,TAR etc) will be compared in both groups as per ADA recommendations and those with <70% data available will be kept on a new device.

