At the end of 3 months direct cross-over of rt-CGMS group to new is-CGMS group and is-CGMS group to new rt-CGMS group will be done and again fructosamine assay shall

be done at the baseline and at the end of 2 weeks. Thereafter, all the 3 groups shall use same glucometer for SMBG till the end of 6 months where HbA1c will be estimated.

[figure not shown]
Hence, for each participant total 6 months of data will be recorded. Individuals will act as their own control thereby removing confounding factors in analysis

[figure not shown]
be done at the baseline and at the end of 2 weeks. Thereafter, all the 3 groups shall use same glucometer for SMBG till the end of 6 months where HbA1c will be estimated.

[figure not shown]
Hence, for each participant total 6 months of data will be recorded. Individuals will act as their own control thereby removing confounding factors in analysis.

[figure not shown]
All these insulins and CGM systems are a part of routine standard care in management of Type-1 Diabetes Mellitus as endorsed by American Diabetic Association in 2022.

FLOW CHART OF STUDY PROTOCOL

OUTCOME VARIABLES TO BE STUDIED

- Glycemic variability as assessed by CGMS
- Daily average insulin requirement per kg body weight
- Fructosamine assay after 2 weeks in rt-CGMS group and is-CGMS group and HbA1c in each of the 3 groups at end of 3 and 6 months respectively;
- Number of hypoglycemic events especially nocturnal and exercise related events;
- Any complications related to CGM;
- Quality of Life by QOLID (Nagpal et al) Questionnaire.

Statistical Analysis:

Statistical analysis will be performed according to the results obtained from parameters. Discrete categorical data will be represented in the form of either a number or a percentage (%), continuous data, assumed to be normally distributed, will be written as either in the form of its mean and standard deviation or in the form of its median and interquartile range, as per the requirement. The normality of quantitative data will be checked by measures of Kolmogorov-Smirnov tests of normality. ANOVA or Mann Whitney U test will be applied to compare 3 groups at a time depending upon the normality of the data. Proportions will be compared using Chi square or Fisher's exact test, depending on their applicability for 3 groups. All the statistical tests will be two-sided and will be performed at a significance level of $P < 0.05$. Analysis will be conducted using IBM SPSS STATISTICS (version 22.0)

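### As the text is ordered, the common 2-week training follows open-label allocation, so knowing the arm could affect its delivery or uptake, and losses during it have no handling rule

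*Combined protocol and SAP*

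**What the plan says.** All references are to the combined protocol and SAP.

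- MATERIALS AND METHODS, item 1 (Study design): "Open label crossover RCT with 3 arms".
- METHODOLOGY, opening sentence: "Participants meeting inclusion criteria will be randomized to rt-CGMS, is-CGMS and SMBG arms". Eligibility is the only stated condition; no run-in or completed training is required. The method is "Randomization will be done using computer generated random number list", with balance across two HbA1c bands. Concealment is not described.
- METHODOLOGY, after the allocation ratio: "Initial training of 2 weeks for all enrolled patients in each of 3 groups about the disease itself, ICR, ISF, carbohydrate counting". The same training also covers how to adjust boluses. Device placement follows in the same paragraph.
- MATERIALS AND METHODS, item 2 (Sample size): "Sample size of 17 is requires for a power of 80% to detect 0.5% change in HbA1c between both groups". The significance level given there is 5%. Allowing for 10% attrition per group, the plan arrives at 20 in each CGM arm and 40 in the SMBG arm.
- Primary objective: HbA1c reduction at 3 months, rtCGM against isCGM. Statistical Analysis names only between-group tests.

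The plan does not say who gives the training, whether those people know the arm, or whether the curriculum is scripted. It defines no analysis set and gives no rule for patients who leave during training.

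**The concern.** Carbohydrate counting, insulin-to-carbohydrate ratios, sensitivity factors and bolus adjustment are taught in order to improve glucose control, so they act on the primary endpoint itself. For the device comparison to be fair, this training has to be the same in every arm. Device wear cannot be masked, but the allocation does not have to be known while the training is given. If it is known, the trainer may adapt content or effort to the assigned device, and participants may engage differently according to what they were assigned. Any resulting HbA1c difference at 3 months would be read as a device effect.

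The order also matters for losses. A patient who leaves during the training fortnight has already been randomised but has never worn a device or started the arm's SMBG schedule. Had training come first, the same patient would not have entered the randomised comparison.

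**Working it through.** **1. Order of events.** Three features of METHODOLOGY point to training after allocation: randomisation is tied to eligibility alone; the training sentence comes later; and it describes training within the three groups, which presupposes that they exist. Against this, the section is not strictly chronological: a sample-size paragraph interrupts it, and an eligibility rule on bolus insulins follows the training sentence. The dates do not decide it either. Last enrolment is 15 August 2023 and last follow-up 15 February 2024, exactly 6 months, so for the last patient the fortnight either lies inside the 6 months or overruns them. Training after allocation is therefore an inference, though the natural one.

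**2. The plan's own sample size.** Inputs: difference 0.5%, power 80%, alpha 0.05, two-sided (Statistical Analysis: "All the statistical tests will be two-sided and will be performed at a significance level of" 0.05), n = 17. No SD is given and the unit of the 17 is not stated, so the figure cannot be reproduced directly. Read as 17 per CGM arm, with the normal approximation:

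SD = 0.5 / (1.960 + 0.842) × √(17/2) = 0.52.

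If 17 were a paired total, the implied SD of the within-patient difference would be 0.5 / 2.802 × √17 = 0.74. The attrition step can be checked: 17 / 0.9 = 18.9, so 19, against 20 planned, which leaves one spare patient per CGM arm.

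**3. What unequal training could do (illustration).** Assume no true device effect, 17 per arm, and a spurious difference b. SE = SD × √(2/17). Type I error = 1 − Φ(1.960 − b/SE) + Φ(−1.960 − b/SE).

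| SD | SE | b | b/SE | Type I error |
|---|---|---|---|---|
| 0.52 (back-solved) | 0.178 | 0.1% | 0.56 | 0.081 + 0.006 = about 9% |
| 0.52 | 0.178 | 0.2% | 1.12 | 0.201 + 0.001 = about 20% |
| 1.0 (assumed) | 0.343 | 0.1% | 0.29 | 0.048 + 0.012 = about 6% |
| 1.0 | 0.343 | 0.2% | 0.58 | 0.084 + 0.005 = about 9% |

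The values of b are assumptions; nothing in the documents supports a particular one.

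**4. Losses during training.** Take 20 randomised per CGM arm, SD 0.52, and 10% later attrition in addition to a training loss t. Completers = 20 × (1 − t) × 0.9. Power = Φ(0.5 / (0.52 × √(2/n)) − 1.960), with n the completers per arm and the unrounded SD (0.5203) used.

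| Training loss t | Completers per arm | Power |
|---|---|---|
| 0% | 18.0 | 82% |
| 5% | 17.1 | 80% |
| 10% | 16.2 | 78% |
| 20% | 14.4 | 73% |

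If the stated 10% already covers losses during training, the first row applies and nothing changes.

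**The case against.** Giving common training after randomisation is a legitimate open-label design. The plan gives one content and one duration for all three groups, so bias needs an actual difference in delivery, uptake or loss, and none is documented. That stands, and it is why the point concerns exposure to bias rather than demonstrated bias.

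The crossover is the strongest counter-argument. The training is given once, and a lasting difference between the two CGM sequences would cancel in a within-patient comparison. But the primary objective is read at 3 months, before the switch; the named tests are between-group; and the text crosses over only the two CGM arms. The comparison that the plan specifies stays exposed.

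Several stronger readings are tempting and should not be made:

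- A reader might infer a size from the cited 158-patient trial of CGM against usual care, whose controls fell by 0.5% at 12 weeks, equal to the difference sought here. The plan's summary does not attribute that fall to training, and no figure for unequal training intensity appears anywhere.
- A reader might take this training to be the strongest shared co-intervention. The documents do not rank it against the daily calls, weekly visits or exercise requirement. The HYPOTHESIS section credits education on patterns seen with CGM, which is a different thing.
- A reader might argue that SMBG participants will disengage and so bias the primary result. That would affect the three-group comparison, not the primary rtCGM against isCGM contrast.
- A reader might infer that patients lost in training will be counted against their arms in the analysis. With no analysis set defined, they could equally be excluded or replaced.

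**Conclusion.** The concern holds as a design weakness that should be corrected, not as a numerical error. On the natural reading of METHODOLOGY, a shared co-intervention that acts on HbA1c is delivered with the arm known, and early losses fall after randomisation with no rule for handling them. For the primary contrast, the remaining route to bias is that training, or loss during it, differs between the two CGM arms.

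The size is unknown. The type I error figures (about 9% and 20% at SD 0.52; about 6% and 9% at SD 1.0) show only how sensitive a comparison of 17 per arm is to a small spurious difference. They rest on the assumed bias, on reading 17 as per arm, and on SDs that the plan does not give. The power loss is conditional on training losses being additional to the assumed 10%. If the missing flow chart shows training before allocation, the point reduces to making the text agree with it.

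**What to change.** In METHODOLOGY, state the sequence explicitly:

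1. Consent and enrol, using the screening HbA1c for eligibility and stratification in all arms.
2. Give the common 2-week training to everyone.
3. Open the allocation, stratified on the screening HbA1c as planned, only on the day the device is fitted or the SMBG schedule starts. Take baseline fructosamine that day.
4. Count the 2-week phase and the 3 months from that day.

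Neither trainer nor participant can then know the arm during training, and losses in the fortnight fall before randomisation. If this order is not feasible, the fallback is a scripted curriculum, trainers unaware of the arm where possible, and a stated analysis set with a rule for patients who leave during training.

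The cost is a protocol wording change with the same staff and content. A few patients will be trained and not randomised: to randomise 80, 80 / 0.95 = 84.2, so 85, must enter training if 5% are lost, and 80 / 0.90 = 88.9, so 89, if 10% are lost. The enrolment or last follow-up date may move by about 2 weeks. The daily calls and weekly visits stay unblinded, so part of the open-label risk remains.

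### The own-control sentence does not hold as written for HbA1c: differential carry-over can bias the month-6 device comparison, and the analysis section should name the month-3 comparison as primary

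*Combined protocol and SAP*

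**What the plan says.** Materials and Methods describes the design as "Open label crossover RCT with 3 arms". The two CGM arms have 20 patients each and exchange devices. The SMBG arm has 40 and never crosses.

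Under Methodology, each device is worn for 2 weeks. After that, "Thereafter the 3 groups shall use SMBG for monitoring glycemic status as in SMBG group and HbA1c will be repeated" at 3 months. Then comes the switch: "At the end of 3 months direct cross-over of rt-CGMS group to new is-CGMS group", with the is-CGM group moving the other way. HbA1c is measured again at 6 months. The section concludes: "Individuals will act as their own control thereby removing confounding factors in analysis".

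The primary objective, rt-CGM against is-CGM, is "Reduction in HbA1c (at the end of 3 months"). The outcome list is wider: "HbA1c in each of the 3 groups at end of 3 and 6 months respectively".

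For continuous data, the Statistical Analysis section lists only between-group tests: "ANOVA or Mann Whitney U test will be applied to compare 3 groups at a time", depending on normality. It names no primary analysis, no primary time point and no within-person method, and it does not mention carry-over.

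The Hypothesis section expects the short-term advantage of rt-CGM to pass into longer-term HbA1c. It also expects 2 weeks of CGM with education to change patients' understanding of their disease in a lasting way.

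**The concern.** The own-control argument works when what happened in period 1 has no unequal influence on period 2. The hypothesis here is that something learned in period 1 lasts, and that it differs by device. That is differential carry-over, so the sentence and the hypothesis conflict.

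What is at stake is how month 6 is read. Someone who trusts the sentence could take a small month-6 device difference as refuting the month-3 result, or a large one as confirming it. Either pattern could come from carry-over alone.

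**Working it through.** **1. Is there a washout?** The last enrolment is on 15 August 2023, with "last follow up on 15th February 2024". That is 184 days for 6 months of data, or 170 (184 − 14) if the 2-week training comes first. The dates leave no room for a separate washout. The weeks without a sensor before the switch number about 13 − 2 = 11, or 9 if training falls inside the 3 months. They remove the sensor but not learned behaviour, and they are the window over which the period-1 HbA1c is formed. The flow chart is not shown, so this rests on text and dates only.

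**2. What carry-over does to each comparison.** Let τ be the true rt-CGM advantage in HbA1c. Let f be the fraction of it that persists to month 6, beyond any carry-over common to both devices. Leave out effects common to both arms, including a common period effect, since they cancel. Mean HbA1c is then:

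- rt-CGM first: −τ at month 3 and −fτ at month 6
- is-CGM first: 0 at month 3 and −τ at month 6

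The rt-CGM advantage is therefore:

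- month 3: 0 − (−τ) = τ
- month 6, raw: −fτ − (−τ) = τ(1 − f)
- raw two-period estimate, if one were made (the mean of the two): τ(1 − f/2)

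With τ = 0.5% (the difference in the sample-size statement, used here as an assumption):

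| f | Month 3 | Raw month 6 | Raw two-period |
|---|---|---|---|
| 0 | 0.50 | 0.50 | 0.50 |
| 0.5 | 0.50 | 0.25 | 0.375 |
| 1 | 0.50 | 0.00 | 0.25 |

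If both devices leave the same effect, such as 0.3%, it cancels and all three estimates stay at 0.50%. If only is-CGM leaves an effect, say 0.2%, month 6 becomes 0.5 + 0.2 = 0.70% and the two-period estimate (0.50 + 0.70)/2 = 0.60%. The direction of bias is therefore not known in advance.

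**3. How precise is the month-3 comparison?** The stated 17 cannot be reproduced, because no SD is given. Read as 17 per arm in a two-sided parallel comparison, it implies SD = 0.5/[(1.96 + 0.84) × √(2/17)] = 0.52 (normal approximation). With 10% attrition, 20 × 0.9 = 18 complete per arm. Power for 0.5% uses SE = SD × √(2/18), a noncentral t with 34 df and a two-sided 0.05 level. All the SDs are assumptions for this trial:

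- SD 0.52 (back-solved above): SE 0.173, power about 80%.
- SD 0.61 to 0.91: SE 0.203 to 0.303, power about 67% to 36%. This range comes from the 24-week parallel trial in the Review of Literature (105 and 53 patients; −0.6, 95% CI −0.8 to −0.3). Its SE is 0.5/3.92 = 0.128, so SD = 0.128/√(1/105 + 1/53) = 0.76, and rounding of the CI limits allows 0.61 to 0.91. It is the SD of an adjusted change, so it is only a rough guide to an unadjusted comparison.
- SD 1.1 (baseline HbA1c spread in the cited trial in patients with normal hypoglycaemia awareness, reading a damaged plus-minus sign): SE 0.367, power about 26%.

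At f = 0.5 the raw month-6 comparison has 29% power at SD 0.52 and 10% at SD 1.1. At f = 1 it has 5%, the test's own error rate.

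**The case against.** The strongest reply is that the main safeguard is already written: the primary objective sits at month 3, and month-6 HbA1c appears only in the outcome list, in neither set of objectives. That stands. It limits the point to one over-broad sentence and an unspecified month-6 analysis.

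Three further replies also stand in part.

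- A common period effect cancels when arms are compared at the same month, so the listed tests need no period term for that purpose. Differential carry-over does not cancel.
- The SMBG arm never crosses, so each CGM sequence against SMBG at month 6 remains a valid randomised comparison. What it estimates is the effect of a sequence of both devices, not of one device.
- A two-period estimate would be more precise than month 3 if carry-over were small. That is a reason to report it alongside, with its assumption stated.

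A reader might infer more than the documents support. They do not show that the primary comparison is biased by carry-over: it precedes the switch, and entry requires no earlier CGM use. They do not show that the plan pools the two periods: no such estimate is specified, and the crossover label only invites one. Nor do they show that month 6 must understate the rt-CGM advantage, since that depends on which device leaves the larger effect.

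**Conclusion.** The concern holds in this limited form. For HbA1c the own-control sentence is wrong as written. Own-control use can remove only stable between-person differences, no listed test uses it, and the hypothesis predicts the kind of lasting, device-dependent effect that would break it. The month-6 device comparison is open to bias in either direction. With an assumed 0.5% advantage, the difference falls to 0.25% if half of the advantage persists and to zero if all of it does. The month-3 comparison is free of carry-over bias, though not of other problems such as dropout.

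The sizes rest on assumed values of τ, f and the SDs, and the no-washout reading rests on text and dates without the flow chart. This is a clarification worth making before analysis, not a flaw in the primary objective.

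**What to change.** 1. In the Statistical Analysis section, add: *The primary analysis is the randomised rt-CGM versus is-CGM comparison of month-3 HbA1c, adjusted for baseline HbA1c.* This means ANCOVA in place of plain ANOVA, and it brings the section into line with the objective.
2. Limit the own-control sentence to *stable between-person differences, assuming no differential carry-over*.
3. Label month-6 and any two-period HbA1c comparison of the devices as supportive. Pre-specify a within-person model on raw HbA1c with terms for participant, device and period. Do not use change from month 3, because that value is itself the period-1 outcome. Show the result beside the month-3 estimate, with the caveat that differential carry-over can bias it either way.
4. Do not use a preliminary carry-over test to choose the analysis.

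The cost is a little more analysis work, with no extra patients or visits. There is no new loss of precision, because month 3 is already the primary time point. Baseline adjustment should recover some: at SD 1.1, power rises from about 26% to 33% or 46% if the correlation of baseline with month-3 HbA1c is 0.5 or 0.7 (assumed; residual SD = 1.1 × √(1 − r²), 33 df).

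### The hypoglycaemic event count is undefined, and if wear-phase counts enter the three-group test, sensor and fingerstick detection are mixed and the comparison could favour SMBG

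*Combined protocol and SAP*

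**What the plan says.** All references are to the combined protocol and SAP.

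- **Objective.** The secondary objectives include "Reduction in hypoglycemic events in adults with Type-1 Diabetes". The objectives open with the stem "To study the effects of rtCGM vs isCGM on".
- **Outcome.** Outcome variables to be studied lists "Number of hypoglycemic events especially nocturnal and exercise related events". The visible text gives no threshold, minimum duration, source, counting window, clock times for nocturnal, or rule linking an event to exercise. The flow chart is among the figures not shown. The thresholds in the literature review belong to cited trials.
- **Nearest specification.** Methodology says that the two-week sensor metrics "will be compared in both groups as per ADA recommendations". These are time-in-range measures for the sensor arms, not event counts.
- **Test.** Statistical Analysis says "ANOVA or Mann Whitney U test will be applied to compare 3 groups at a time", with no exception for the event count.
- **Monitoring during wear (Methodology).** In the rt-CGM arm, "finger-prick blood glucose will also be monitored by glucometer (SMBG) 3 times on day 1 and then at least 2 times per day". The SMBG arm tests four times a day, "Before breakfast, Before Lunch, and Before Dinner and post meal (after any one meal on rotational basis"), plus a seven-point profile each Sunday. No fingerstick number is given for the is-CGM arm. After wear, all three arms follow the SMBG arm's schedule.
- **Contact.** "During this 2 week intervention phase all the patients will be monitored daily telephonically along with once in a week follow-up visit". The calls are not named as a source of events.

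**The concern.** An event count depends on how often one looks. During the two-week wear phase the arms look at very different rates. A count taken from whatever each arm happens to record would therefore differ between arms even if the true event rates were equal. The SMBG arm would tend to record fewer events because some of its lows go undetected. The gap is widest at night, which the outcome line singles out and the ordinary daily schedule does not sample. If CGM truly reduces events, the same mechanism would hide or shrink that benefit.

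Two obvious repairs do not work as they stand. Counting only meter readings during wear leaves unequal numbers of tests by arm. Relying on the calls without a rule can bring in lows that only an rt-CGM alarm revealed; the Background device table gives alarms for rt-CGM and none for is-CGM.

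**Working it through.** The plan gives no figure for this outcome to reproduce; its sample size concerns HbA1c.

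**1. Readings per arm in 14 days** (Background device table; Methodology)
- rt-CGM: 1440/5 × 14 = 4,032. is-CGM: 1440/15 × 14 = 1,344.
- SMBG: (6×4 + 7) × 2 = 62 if the Sunday profile replaces that day's tests, or (7×4 + 7) × 2 = 70 if it is added.
- rt-CGM arm, minimum meter tests: 3 + 13×2 = 29.

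**2. Chance that a scheduled fingerstick falls inside a low of L minutes.** Assuming random timing, this is (n/14) × L/1440.

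| Tests in 14 days | 20-min low | 60-min low |
|---|---|---|
| 62 (SMBG) | 6.2% | 18.5% |
| 70 (SMBG) | 6.9% | 20.8% |
| 29 (rt-CGM, meter only) | 2.9% | 8.6% |

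**3. Adding symptom-prompted tests.** If a share s of lows prompts a test, SMBG detection is s + (1−s)p, with p = 0.065 (20 min) or 0.196 (60 min). The documents do not give s.

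**4. False-positive rate.** Simulation of 20/20/40 patients with equal true rates, every event seen in the sensor arms, SMBG counts thinned to the detection share, and one-way ANOVA at 0.05. Assumed means are 1, 2.7 and 5.4 events per 14 days. The last is half of the 10.8 per 28 days in the cited rt-CGM trial in impaired awareness or severe hypoglycaemia, so it is an upper anchor. The assumed coefficient of variation is 0.93 (10.0/10.8, same trial) or 1.3. Ranges span all settings.

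| Share s prompting a test | Detection, 20 / 60 min | Rejection, 20 min | Rejection, 60 min |
|---|---|---|---|
| 0 | 0.065 / 0.20 | 98–100% | 86–100% |
| 25% | 0.30 / 0.40 | 68–100% | 48–96% |
| 50% | 0.53 / 0.60 | 28–73% | 21–54% |
| 75% | 0.77 / 0.80 | 9–19% | 8–16% |
| 90% | 0.91 / 0.92 | 5–7% | 5–7% |

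With complete SMBG detection the rate is 4–5%, so the excess comes from detection alone. A three-group rank test (Kruskal-Wallis) behaves similarly: 23–53% at s = 50% for 20-min lows.

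**5. Incomplete sensor capture.** Methodology replaces a device only below 70% data. If the sensor arms catch 70% of events (an assumption at that floor), rejection at s = 50% falls from about 22–64% to 7–17%, and at s = 75% it is 4–5% (spread applied to the rates). At s = 90%, SMBG detection of 0.91 exceeds 0.70 and the bias reverses.

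**6. A true CGM benefit.** Take event ratios to SMBG of 0.28 (rt-CGM, the same cited trial) and 0.62 (is-CGM, from a cited 38% reduction in time rather than events). With complete sensor capture, the expected observed ratio is the true ratio divided by SMBG detection. At s = 50%:
- 20-min lows: 0.28/0.5325 = 0.53 and 0.62/0.5325 = 1.16.
- 60-min lows: 0.28/0.598 = 0.47 and 0.62/0.598 = 1.04.

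The rt-CGM benefit shrinks and the is-CGM benefit disappears.

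**7. Sampling interval, rt-CGM versus is-CGM.** If one low reading counts, a 15-min interval catches min(1, L/15) of lows, so only those under 15 min are affected. If low readings must span 15 min, is-CGM catches (L−15)/15 (33% at 20 min, 67% at 25 min, 100% at 30 min), while native rt-CGM readings catch 100% from 20 min.

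**The case against.** The strongest objection is that the plan may never intend a three-arm event comparison. Events sit under the rt-CGM versus is-CGM stem. The three-group sentence is generic: it makes no exception for fructosamine or sensor-assessed variability either, although fructosamine is planned only in the sensor arms and SMBG patients wear no sensor. For HbA1c the outcome list names all three groups; the event line does not. This stands as a reason to state the risk conditionally. It does not remove the risk, because the fructosamine line names its two arms and the event line names none.

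A reader might infer that SMBG would look safest. The documents do not support that. It needs equal true rates, whereas the Background regards rt-CGM's advantage over SMBG on events as established. With true ratios of 0.28 and 0.62 and an assumed 6.85 events per 14 days (half of 13.7 per 28 days in the cited trial's controls), SMBG has the lowest mean in 97% of simulated trials at 15% detection, 62% at 25%, but 1% at 50%. Even with equal rates and full sensor capture, it is lowest in about 36–44% of trials when 90% of lows prompt a test, against 27–30% with complete detection.

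The near-100% figures are also the extreme case. Participants have a Gold score below 4, are taught the symptoms and are called daily, so some lows would be noticed and tested.

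Finally, a reader might infer that is-CGM would look safer than rt-CGM. That needs a 15-minute duration rule, which the plan does not state, and it touches only lows of 15–30 minutes, whose share is unknown.

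**Conclusion.** The concern holds in a conditional form. The event count is undefined in the visible text, and the only stated test for quantitative outcomes does not exclude SMBG from it. If wear-phase counts enter that test, the comparison could be biased towards SMBG, most for nocturnal events, and could hide or shrink a real CGM benefit.

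The direction assumes that SMBG detects a smaller share of lows than the sensors do. The size rests on the share of lows that prompt a test, the length of lows, the event rate and sensor capture, none of which the documents give for this population. The plausible range runs from near-certain false significance to none, with reversal possible. The problem is confined to the wear phases and to a secondary outcome; the HbA1c comparison is untouched. The change should be made, but the trial's main result does not depend on it.

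**What to change.** 1. Analyse sensor-derived wear-phase counts for rt-CGM versus is-CGM only, within person over both crossover periods, with period in the model. Do not pool them with SMBG counts.
2. Pre-state one event definition for both devices: glucose threshold, minimum duration, clock window for nocturnal and link window for exercise-related. Apply it on a common 15-min grid, and say whether one or two consecutive low readings qualify.
3. Base any three-arm comparison on events recorded the same way in every arm. One option is symptomatic events asked for in the daily calls during wear, noting whether symptoms came before any device reading or alarm. The other is symptomatic or meter-confirmed events from the end of wear to month 3, when all arms share one SMBG schedule. Do not compare meter-confirmed counts across arms during wear. Report tests per day by arm.
4. Report months 3–6 separately, because each CGM arm has by then moved to its second device.

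**Cost.** SAP wording, a small resampling step, and an event log used in the planned calls and for about 9–11 weeks after wear (13 weeks minus 2, or minus 4 if month 3 is counted from before the training). No extra sensors or visits are needed.

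**Downsides.** There is no three-arm sensor comparison during wear. Some short rt-CGM dips are dropped; if two consecutive readings are required, both devices miss about 67% of 20-min and 33% of 25-min lows. Symptomatic counts miss unnoticed lows in every arm.
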